**Figure 1: Study Overview**

### 3.1 Inclusion Criteria

A subject will be eligible for inclusion in this study only if all of the following criteria apply:

- Capable of giving written informed consent, which includes compliance with the requirements and restrictions listed in the consent form
- Patients must have histologically or cytologically confirmed clinically detected, node involved Stage IIIB/C/D melanoma by AJCC version 8 and surgically resectable disease. The definition of resectability can be determined by the patient's surgical oncologist and verified via discussion at Multidisciplinary Tumor Conference attended by melanoma medical and surgical oncology staff. Resectable tumors are defined as having no significant vascular, neural or bony involvement that would preclude complete resection or necessitate the use of adjuvant radiation. Only cases where a complete surgical resection with tumor-free margins can safely be achieved are defined as resectable.
- BRAF mutation-positive melanoma (V600E or V600K) based on report from a CLIA certified laboratory.
- Patients must have measurable disease, defined by RECIST 1.1
- Patients who have been previously treated in the adjuvant setting with ipilimumab or interferon alpha or investigational vaccines for melanoma will be eligible for treatment after a 28 day wash-out period
- Patients who have previously received anti PD-1 in the adjuvant setting will be allowed if it has been six months or longer since previous drug exposure
- Age >=18 years
- ECOG performance status 0-1 (See Appendix A)
- Women of childbearing potential, defined as all women physiologically capable of becoming pregnant will be required to use highly effective methods of contraception during dosing and for 150-days after stopping treatment with spartalizumab. Highly effective contraception methods include:
  - Highly effective contraception methods include:
    - a. Total abstinence (when this is in line with the preferred and usual lifestyle of the subject). Periodic abstinence (e.g., calendar, ovulation, symptothermal, post-ovulation methods) and withdrawal are not acceptable methods of contraception.
    - b. Female sterilization (have had surgical bilateral oophorectomy with or without hysterectomy), total hysterectomy, or tubal ligation at least six weeks before taking study treatment. In case of oophorectomy alone, only when the reproductive status of the woman has been confirmed by follow up hormone level assessment.
    - c. Male sterilization (at least 6 months prior to screening). The vasectomized male partner should be the sole partner for that subject
    - d. Placement of a non-hormonal intrauterine device (IUD) or intrauterine system (IUS) with a documented failure rate of less than 1% per year.

Notes:

- Double-barrier contraception: condom and occlusive cap (diaphragm or cervical/vault caps) with a vaginal spermicidal agent (foam/gel/cream/suppository) are not considered highly effective methods of contraception.
- Hormonal-based methods (e.g., oral contraceptives) are not considered as highly effective methods of contraception due to potential drug-drug interactions with dabrafenib.

- Women are considered post-menopausal and not of child bearing potential if they have had 12 months of natural (spontaneous) amenorrhea with an appropriate clinical profile (i.e. age appropriate, history of vasomotor symptoms) or have had surgical bilateral oophorectomy (with or without hysterectomy), total hysterectomy, or tubal ligation at least six weeks ago. In the case of oophorectomy alone, only when the reproductive status of the woman has been confirmed by follow up hormone level assessment is she considered not of childbearing potential.
- Sexually active males must use a condom during intercourse while on treatment and for 150 days after stopping treatment with spartalizumab and should not father a child in this period. A condom is required to be used by vasectomized men as well during intercourse in order to prevent delivery of the drug via semen
- Organ function as defined below in Table 1:

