### 3.0 STUDY DESIGN

[figure not shown]
This is an open-label single arm Phase II study that aims to examine the strategy of altering adjuvant therapy depending on pathologic response to neoadjuvant dabrafenib and trametinib therapy. Clinical stage III B/C/D BRAF V600E/K mutation with resectable disease will be enrolled. Patients will undergo 8 weeks of neoadjuvant dabrafenib and trametinib, followed by restaging scans and then definitive surgery if disease remains resectable. Surgical pathology will be analyzed for pathologic complete response (pCR), which is defined as absence of any residual tumor by H&E assessment.

Near pCR will be defined as less than 10% viable melanoma in the surgical specimen. Pathologic partial response (pPR) is defined as less than 50% viable tumor in the surgical specimen. No pathologic response (pNR) is defined as  $\geq 50\%$  viable tumor in the surgical specimen.

Patients who achieve a pCR will continue with adjuvant dabrafenib and trametinib for an additional 44 weeks in order to complete a total 1 year of therapy. Patients who do not achieve a pCR after 8 weeks of neoadjuvant dabrafenib and trametinib will receive dabrafenib, trametinib and spartalizumab in the adjuvant setting for a total of 44 weeks. Patients with no resectable disease after neoadjuvant therapy will be removed from the study and replaced.

Longitudinal blood and tumor will be collected in accordance with the study schedule.

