**Table 5 Dose Modification Guidelines – General**

CTCAE Grade	Action and Dose Modification
Grade 1 or Grade 2 (tolerable)	Continue study treatments at same dose level (no dose modification)
Grade 2 (Intolerable)	
1 st or 2 nd occurrence	Interrupt study treatments until toxicity resolves to $\leq$ grade 1 then restart at same dose level
3 rd or occurrence	Interrupt study treatments until toxicity resolves to $\leq$ grade 1 then restart at next lower dose level
4 th or greater occurrence	Interrupt study treatments until toxicity resolves to $\leq$ grade 1 then restart at two dose levels lower than the starting dose or discontinue treatments per investigator discretion
Grade 3	
1 st occurrence	Interrupt study treatments until toxicity resolves to $\leq$ grade 1 or baseline then restart at next lower dose level
2 nd occurrence	Interrupt study treatments until toxicity resolves to $\leq$ grade 1 or baseline then restart at two dose levels lower than the starting dose
3 rd occurrence	Discontinue treatments.
Grade 4	
1 st occurrence	Discontinue treatments

For dabrafenib and/or trametinib related adverse events: if following an interruption of dabrafenib and trametinib, an AE doesn't recover to  $\leq$  Grade 1 or baseline within 4 weeks, dabrafenib and trametinib must be discontinued.

No dose reductions are allowed for spartalizumab. Dose interruption for spartalizumab includes delaying or withholding the treatment for any reason as well as an interruption of treatment during an infusion. All dose interruptions and the reason for the dose interruption must be recorded. Dose interruption for spartalizumab includes delaying or withholding the treatment for any reason as well as an interruption of treatment during an infusion. Subjects with adverse events suspected to be related to spartalizumab including those of potential immune-mediated etiology (irAE) must be permanently discontinued from spartalizumab if (1) the AE doesn't recover to  $\leq$  Grade 1 or baseline within 12 weeks and/or (2) the dose of steroids (for the management of irAE) remains  $> 10$  mg/day prednisone or equivalent for  $> 12$  weeks. The 12 week timeframe will begin from the time the irAE reaches a grade that leads to spartalizumab interruption.

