### ***SAE REPORTING***

The principal investigator has the obligation to report all serious adverse events to the FDA (if applicable), IRB, and Novartis Patient Safety Department (***For patients taking Novartis drugs***).

All events reported to the FDA by the investigator are to be filed utilizing the Form FDA 3500A (MedWatch Form), if applicable.

- To ensure patient safety, every SAE, regardless of suspected causality, occurring after the patient has provided informed consent and until at least 150 days after the patient has stopped study treatment or until the start of a new anti-neoplastic

medication if sooner than 150 days must be reported to Novartis within 24 hours of learning of its occurrence. If a subject starts a post-treatment antineoplastic therapy, then only adverse events suspected to be related to study treatment should be collected out to 150 days after discontinuation of PDR001. Reporting to Novartis should also occur within 30 days after the last dose of dabrafenib or 120 days after the last dose of trametinib, if the subject continued the combination partner more than 150 days after the last dose of PDR001). Information about all SAEs is collected and recorded on a Serious Adverse Event Report Form. The investigator must assess and record the relationship of each SAE to each specific study treatment (if there is more than one study treatment), complete the SAE Report Form in English, and **send the completed, signed form along with the Novartis provided cover sheet to the Novartis Patient Safety department by email ([contact]) within 24 hours.**

Any additional information for the SAE including complications, progression of the initial SAE, and recurrent episodes must be reported as follow-up to the original episode within 24 hours of the investigator receiving the follow-up information. An SAE occurring at a different time interval or otherwise considered completely unrelated to a previously reported one should be reported separately as a new event.

Any SAEs experienced after the reporting period described above period should only be reported to Novartis if the investigator suspects a causal relationship to the study treatment.

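### Section 3.1 counts post-treatment contraception only from stopping spartalizumab, so patients who never receive it have no stated post-dose period and those who stop it early have a shortened one

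*Combined protocol and SAP*

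**What the plan says.** Section 3.1 (Inclusion Criteria) sets the contraception rule in two bullets. Women of childbearing potential "will be required to use highly effective methods of contraception during dosing and for 150-days after stopping treatment with spartalizumab". For men the text is: "Sexually active males must use a condom during intercourse while on treatment and for 150 days after stopping treatment with spartalizumab". Neither bullet gives a period tied to the last dose of dabrafenib or trametinib, and no other section in the available documents does.

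Section 3.0 creates two groups who never receive spartalizumab. The first is the pCR group: "Patients who achieve a pCR will continue with adjuvant dabrafenib and trametinib for an additional 44 weeks". The second leaves after the neoadjuvant phase: "Patients with no resectable disease after neoadjuvant therapy will be removed from the study and replaced".

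Spartalizumab can also be stopped on its own. Below Table 5 in Section 3.3.2, patients whose suspected spartalizumab-related event does not resolve within 12 weeks, or who need more than 10 mg/day prednisone for over 12 weeks, "must be permanently discontinued from spartalizumab". Section 3.8.2 adds a stop when prednisone cannot be brought below 10 mg/day before the next dose.

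Safety reporting uses a different starting point. Section 5.0 records adverse events to 150 days after the last dose of study drug, and Section 5.3 captures serious adverse events over the same span. The company-reporting text in Section 5.3 adds windows "within 30 days after the last dose of dabrafenib or 120 days after the last dose of trametinib", applying "if the subject continued the combination partner more than 150 days after the last dose of PDR001". PDR001 is spartalizumab.

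**The concern.** The post-dose contraception clock starts when one particular drug stops, yet by design a substantial share of patients never take that drug. Read literally, the clock has no start date for them. In the non-pCR group, the time covered after the last dabrafenib/trametinib dose depends on when a different drug was stopped. Two patients with the same last dabrafenib/trametinib dose can therefore have different obligations.

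The company-reporting text shows that the authors foresaw the partner drugs outlasting spartalizumab by more than 150 days. They provided for that case in serious adverse event reporting but not in Section 3.1. What is at stake is a participant-safety instruction.

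**Working it through.** The plan states no figure of its own to reproduce here. The check is a reading of the rule for each group, followed by date arithmetic.

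**Patients who never receive spartalizumab.** Section 3.1 requires contraception during dosing, which covers time on dabrafenib and trametinib. After the last dose the only stated period is 150 days from stopping spartalizumab. These patients never start it, so no post-dose period is defined.

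- pCR patients: Section 7.0 plans 45 patients with about 60% not reaching pCR, so 45 × (1 − 0.60) = 18.
- Section 1.2 reports a 58% pCR rate in the interim cohort of the earlier trial, which would give 45 × 0.58 = 26.1, about 26. The later update in the same section gives 40%, which matches the planning value.
- Patients removed as unresectable: the documents give no expected number.

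**Non-pCR patients who stop spartalizumab early.** Inputs:

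- Infusions every 28 days, marked at Weeks 12 to 48 in Table 12.
- End of dabrafenib/trametinib after 8 + 44 = 52 weeks, that is day 7 × 52 = 364.
- Post-dose period of 150 days (Section 3.1), counted here from the last infusion.

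For a last infusion at Week N, the days of contraception left after the last dabrafenib/trametinib dose are max(0, 7N + 150 − 364).

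| Last infusion (week) | 7N + 150 − 364 | Days left |
|---|---|---|
| 12 | −130 | 0 |
| 16 | −102 | 0 |
| 20 | −74 | 0 |
| 24 | −46 | 0 |
| 28 | −18 | 0 |
| 32 | 10 | 10 |
| 36 | 38 | 38 |
| 40 | 66 | 66 |
| 44 | 94 | 94 |
| 48 (on schedule) | 122 | 122 |

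The break point is (364 − 150) / 7 = 30.6 weeks. Infusion visits have a window of ±7 days, which moves each raw figure by up to 7. Week 28 still gives 0 (−18 + 7 = −11) and Week 32 still gives a positive number (10 − 7 = 3).

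**With 150 days from the last dose of any study drug.** Every patient whose last drug is dabrafenib or trametinib would have 150 days after it. The gain is 150 days for pCR patients and for last infusions up to Week 28. It is 140, 112, 84 and 56 days at Weeks 32, 36, 40 and 44, and 150 − 122 = 28 days for an on-schedule patient.

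**The case against.** The strongest objection is that the operative rule may lie elsewhere. Section 3.1 makes eligibility include "compliance with the requirements and restrictions listed in the consent form". That form was not available for review and may give a post-dose period for dabrafenib and trametinib. This stands, and it limits the point to the wording of Section 3.1. A reader might infer that participants receive no post-dose instruction at all; the documents cannot show that.

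Second, nothing in the documents says that a post-dose period is needed for dabrafenib or trametinib, or how long it should be. This also stands. A reader might take the 30- and 120-day windows in Section 5.3 as washout periods and measure the contraception rule against them. They are windows for reporting serious adverse events, and the documents give them no other meaning. The point therefore rests on the starting date of a rule that the protocol itself chose to set, and no duration is claimed to be correct.

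Third, the early-stopper group may be small. Section 3.3.1 reports that 17% of patients in the metastatic study stopped the triplet for toxicity. It does not say how many stopped spartalizumab alone and kept the other two drugs, which is the only group affected. Some rules in Section 3.3.2 stop dabrafenib and trametinib as well. No count can be given for this group, and the table shows only what the rule would require in each case.

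It could also be said that sites will simply apply 150 days to everyone. That may happen in practice, but the text names one drug, and a patient who never received it cannot stop it.

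**Conclusion.** The point holds as a wording defect in a participant-safety rule and should be fixed. Section 3.1 leaves patients who never receive spartalizumab without a stated post-dose contraception period. It also shortens the period for those who stop spartalizumab early and continue the other two drugs, to 0 days for a last infusion at Week 28 or earlier and to 10 to 94 days at Weeks 32 to 44, against 122 days on schedule.

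The figures rest on these assumptions:

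- Dabrafenib and trametinib run to Week 52.
- Stopping spartalizumab means the last infusion. Dating it from a later decision to discontinue would leave more days.
- The pCR rate is the planned 40%. The figure of 18 is a point estimate for all pCR patients. It should not be read as a ceiling, because Section 7.0 itself allows for a higher pCR rate; nor is it a count of patients at reproductive risk, because the shares of childbearing potential or sexually active are not given.

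A reader might also infer that contraception lapses during dabrafenib/trametinib treatment. It does not: both bullets cover the whole time on treatment, and the gap begins only after the last dose. The endpoint, sample size and analysis are not affected.

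**What to change.** In both Section 3.1 bullets, count the period from the last dose of any study drug. Either of two forms would do:

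- 150 days after the last dose of any study drug for all patients, which matches the adverse-event windows in Sections 5.0 and 5.3.
- A period for each drug, with the latest end date applying: 150 days for spartalizumab, and dabrafenib and trametinib periods set by the sponsor.

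The words "last dose" would also settle whether stopping means the final infusion or the decision to discontinue. Check the consent form and align it if it differs.

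The cost is a protocol wording amendment, plus a consent form change if needed. No visits are added. The downside is a longer contraception obligation for some patients: under the 150-day form, up to 150 more days for those not on spartalizumab near the end of treatment and 28 more for on-schedule patients. Per-drug periods could make it shorter.

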**Table 1: Organ function criteria**

Hematological	
Absolute neutrophil count (ANC)	$\geq 1500/\mu L$
Platelets	$\geq 100\,000/\mu L$
Hemoglobin	$\geq 9.0\text{ g/dL}$ or $\geq 5.6\text{ mmol/L}^a$
Renal	
Creatinine OR Measured or calculated b creatinine clearance (GFR can also be used in place of creatinine or CrCl)	$\leq 1.5 \times \text{ULN}$ OR $\geq 30\text{ mL/min}$ for participant with creatinine levels $> 1.5 \times$ institutional ULN
Hepatic	
Total bilirubin	$\leq 1.5 \times \text{ULN}$ OR direct bilirubin $\leq \text{ULN}$ for participants with total bilirubin levels $> 1.5 \times \text{ULN}$
AST (SGOT) and ALT (SGPT)	$\leq 2.5 \times \text{ULN}$
Coagulation	
International normalized ratio (INR) OR prothrombin time (PT) Activated partial thromboplastin time (aPTT)	$\leq 1.5 \times \text{ULN}$ unless participant is receiving anticoagulant therapy as long as PT or aPTT is within therapeutic range of intended use of anticoagulants
ALT (SGPT)=alanine aminotransferase (serum glutamic pyruvic transaminase); AST (SGOT)=aspartate aminotransferase (serum glutamic oxaloacetic transaminase); GFR=glomerular filtration rate; ULN=upper limit of normal.	
a Criteria must be met without erythropoietin dependency and without packed red blood cell (pRBC) transfusion within last 2 weeks.	
b Creatinine clearance (CrCl) should be calculated per institutional standard.	

### 3.2 Exclusion Criteria

A subject will not be eligible for inclusion in this study if any of the following criteria apply:

- Currently receiving cancer therapy (chemotherapy, radiation therapy, immunotherapy, or biologic therapy) or investigational anti-cancer drug within 28 days
- Evidence of metastatic melanoma or patients with only in-transit metastases without involved nodes
- Prior BRAF or MEK inhibitor use
- Prior anti PD-1 or anti PD-L1 inhibitor use in last 6 months
- Prior malignancy active within the previous 2 years except for patient's prior diagnosis of melanoma and locally curable cancers that have been apparently cured, such as basal or squamous cell skin cancer, superficial bladder cancer, or carcinoma in situ of the prostate, cervix, or breast with local control measures (surgery, radiation).
- Subjects with active, known or suspected autoimmune disease. Subjects with vitiligo, type I diabetes mellitus, residual hypothyroidism due to autoimmune condition only requiring hormone replacement, psoriasis not requiring systemic treatment, or conditions not expected to recur in the absence of an external trigger are permitted to enroll.
- Subjects with a condition requiring systemic treatment with either corticosteroids (> 10 mg daily prednisone equivalents) or other immunosuppressive medications within 14 days of study drug administration. Inhaled or topical steroids and adrenal replacement doses > 10 mg daily prednisone equivalents are permitted in the absence of active autoimmune disease.
- Any positive test result for hepatitis B or C and HIV virus indicating acute or chronic infection
- Known history of testing positive for human immunodeficiency virus or known acquired immunodeficiency syndrome
- History of severe hypersensitivity reaction to any monoclonal antibody
- History of Central serous retinopathy (CSR) or retinal vein occlusion (RVO), or predisposing factors to RVO or CSR (e.g. uncontrolled glaucoma or ocular hypertension, uncontrolled systemic disease such as hypertension, diabetes mellitus, or history of hyperviscosity or hypercoagulability syndromes). Presence of active gastrointestinal disease or other condition that will interfere significantly with the absorption, distribution, metabolism, or excretion of drugs. QTc interval  $\geq$  480 msec ( $\geq$  500 msec for subjects with Bundle Branch Block) Uncontrolled arrhythmias
- Class II, III, or IV heart failure as defined by the New York Heart Association (NYHA) functional classification system
- Pregnant or lactating female
- Unwillingness or inability to follow the procedures required in the protocol
- Uncontrolled diabetes, hypertension or other medical conditions that may interfere with assessment of toxicity

Subjects with known glucose 6 phosphate dehydrogenase (G6PD) deficiency

### **3.3 TRIAL TREATMENT – Study Drugs and Administration Details**

**Table 2a: Neoadjuvant Treatment**

Study Drug	Dose
Dabrafenib	150mg by mouth twice daily
Trametinib	2mg by mouth daily

**Table 2b: Adjuvant Treatment of pCR patients**

Study Drug	Dose
Dabrafenib	150mg by mouth twice daily
Trametinib	2mg by mouth daily

**Table 2c: Adjuvant Treatment of non pCR Patients**

Study Drug	Dose
Dabrafenib	150mg by mouth twice daily
Trametinib	2mg by mouth daily
Spartalizumab	400mg IV every 28 days

**Table 3: Trial Treatments and Description****Table 3a: Neoadjuvant Treatment**

Product	Dose	Dose Frequency	Route of Administration	Appearance	Storage Conditions (per label)
Dabrafenib	150 mg	BID	By mouth	Capsules for oral use	Refer to study
					treatment label
Trametinib	2mg	Daily	By mouth	Tablets for oral use	Refer to Associated IB

**Table 3b: Adjuvant Treatment of pCR patients**

Product	Dose	Dose Frequency	Route of Administration	Appearance	Storage Conditions (per label)
Dabrafenib	150 mg	BID	By mouth	Capsules for oral use	Refer to Associated IB
Trametinib	2mg	Daily	By mouth	Tablets for oral use	Refer to Associated IB

